- x For subjects who consent to participate in the CSF longitudinal substudy. Visit 13 (or ED) also includes blood PK and PD assessments and so the subject will be dosed at the clinic on these days. A CSF sample will be collected by LP between 4 and 8 hours postdose and at the same time of day as the subject's Screening LP (± 1 hour). The CSF sample will be taken with the subject fasting (preferred) or at least 2 hours after the most recent meal. A gravity drip collection method must be used. If performed on the same day as the cognitive tests, the LP will be performed after the cognitive tests; the subject should rest and drink some fluid to hydrate after the cognitive tests and before the LP. Subjects will be encouraged to stay at the site after completion of LP for medical observation. The CSF sample will not be taken at the ED Visit if this visit occurs within 3 months of a previous CSF sample. If at an ED Visit, the subject has already stopped study drug, then no dosing will take place, but the CSF sample will still be collected unless it was already collected within the past 3 months. Subjects receiving concomitant anticoagulation/antiplatelet therapy should have prothrombin time and INR (derived from prothrombin time) prior to LP; if they are assessed by the investigator to be at risk for bleeding, they are to be excluded from CSF collection. Note that subjects who are assessed by both amyloid PET and CSF are required to wait for a minimum of 48 hours between the 2 procedures. (revised per Amendment 01)
- y Subjects reporting AEs relating to abnormal dreams, nightmares, or sleep terror will be questioned on the nature, frequency, and impact of these events.
- z AEs that might indicate signals of possible drug abuse potential require a more detailed follow-up through completion of a specific eCRF form (Possible drug abuse potential form/ questionnaire); categories and examples of AEs indicating signals of possible drug abuse are provided in [Appendix 3](#). (revised per Amendments 01)
- aa The 1st dose of study drug will be given to the subject at the study site and the subject will be encouraged to stay at the site for an appropriate period of time for postdose medical observation.

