Plasma concentrations of elenbecestat (E2609) that may extend to the key metabolites M1, M2, and M5 will be measured by a validated assay using liquid chromatography method using tandem mass spectrometry.

A β (1-x) and other relevant biomarkers will be measured in the blood samples collected at times that match the PK draws and during the Followup Period. (revised per Amendment 01)

Statistical Methods

All statistical analyses will be performed by the sponsor or designee after the study is completed and the database is locked and released for unblinding.

Study Endpoints

Primary Endpoint

- Change from baseline in the CDR-SB at 24 months

Secondary Endpoints

- Time to worsening of CDR scores by 24 months (eg, the worsening of global CDR score is defined as an increase from baseline by at least 0.5 points on the global CDR scale on 2 consecutive scheduled visits at which global CDR is undertaken)
- Time to conversion to dementia by 24 months for subjects who were not clinically staged as dementia at Baseline based on clinical diagnosis
- The rate of change over time (mean slope) based on CDR-SB score over 24 months
- Change from baseline in CDR-SB at 27 months (ie, 24 months of treatment plus 3 months posttreatment follow-up)
- Change from baseline in ADAS-cog₁₄, MMSE, and FAQ at 24 months
- Change from baseline in ADAS-cog₁₄ Word List (immediate recall and delayed recall) at 24 months

Biomarker Endpoints

- Change from baseline in amyloid PET SUVR composite at 24 months for brain amyloid levels
- Change from baseline in CSF biomarkers t-tau and p-tau at 24 months
- Change from baseline in CSF amyloid biomarkers A β (1-40), A β (1-42), and A β (1-x) at 24 months
- Change from baseline in total hippocampal volume at 24 months using vMRI

- Change from baseline in the preservation of connectivity on fMRI at 24 months

Exploratory Endpoints

- Time to change of concomitant AD treatment (ie, dose increase and/or initiation of treatment with AChEI or memantine after randomization) by 24 months
- The proportion of subjects at 24 months who received dose increases and/or initiation of treatment with AChEI or memantine after randomization
- The rate of change over time (mean slope) based on NPI-10 item score over 24 months
- Change from baseline in NPI-10 item at 24 months
- Change from baseline in EQ-5D (subject self-reported, study partner self-reported, and subject measured by proxy) and QOL-AD (subject and study partner) at 24 months

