9.5.1.4 Pharmacokinetic, Pharmacodynamic, Pharmacogenomic, and Other Biomarker Assessments

9.5.1.4.1 PHARMACOKINETIC ASSESSMENTS

Blood samples will be collected for the determination of the concentrations of elenbecestat (E2609) in all randomized subjects. Analyses of metabolite concentrations may be performed, depending on emerging data from other studies with elenbecestat (E2609).

Samples from all subjects receiving active treatment will be analyzed. In addition, a predetermined percentage of placebo samples will be analyzed. Remaining placebo samples

will be held in storage in the event that further confirmatory analysis is requested. Plasma concentrations of analytes will be quantified by liquid chromatography with tandem mass spectrometry methodology using a previously validated assay.

Blood samples will be collected as specified in [Table 2](#) and [Table 3](#). Two plasma PK samples will be obtained at each of the following visits: 1 sample at predose (trough) and another sample 1 to 6 hours postdose at Visits 3, 4, 6, 7, 9, and 11 and another sample 4 to 8 hours postdose at Visit 13 (or ED). Therefore, subjects or their study partners must be instructed not to take their study drug at home on the day the PK sampling is performed. Instead, subjects will take the study drug at the clinic after collection of the predose PK sample. At Visit 13 (or ED) the PK blood sample should be collected shortly before or after completing the LP for subjects participating in the CSF substudy. If at an ED Visit, the subject has already stopped study drug, then no dosing will take place, but the trough PK sample will still be collected. For subjects participating in the CSF substudy who have stopped taking study drug prior to the ED visit, the LP should be performed at approximately the same time as at the Screening Visit, and then a trough PK sample will be collected either shortly before or shortly after the LP.

Blood will also be drawn where possible at the first report of an SAE or severe unexpected AE and at its resolution.

See the laboratory manual (to be supplied to study sites) for a description of the collection, handling, and shipping procedures for PK samples.

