- j: The blood samples taken for PD and exploratory biomarkers should be collected at fasting or at least 2 hours after the most recent meal. For subjects who are going to provide a CSF sample at Tier 5 for amyloid eligibility and/or PD baseline purposes, the timing of the blood draw for PD and exploratory biomarkers should be at approximately the same time of day as planned for the LP.
 - k: Viral screen to include HCVAb (Hepatitis C) and HBsAg (Hepatitis B).
 - l: Only required for female subjects of child-bearing potential
 - m: For subjects who are approved for rescreening, MRI and vMRI need not be repeated if the date of the rescreen is no more than 90 days from the date of the original screening MRI.
 - n: PET scanning will be performed with a locally approved amyloid imaging agent (eg, Amyvid, if available or an agent under clinical investigation if no agents are approved locally); for subjects participating in the PET substudy, the imaging agent must remain unchanged throughout the study. Subjects who are assessed by both amyloid PET and CSF are required to wait for a minimum of 48 hours between the 2 procedures (revised per Amendment 01). A positive amyloid result is needed for only 1 of the 2 amyloid eligibility procedures to confirm eligibility (ie, even if 1 of the 2 results is negative for amyloid, the subject would still be eligible under the other, positive result). For subjects who are approved for rescreening, the amyloid PET need not be repeated for eligibility if confirmed amyloid positive during the original screening procedure. If a rescreened subject will participate in the longitudinal PET substudy, quantitative PET collection should be repeated if the original PET collection was done greater than 6 months from the date of the original screening procedure

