- ^t PET scanning (if subject has consented to optional substudy) will be performed with a locally approved amyloid β imaging agent, eg, Amyvid, if available or an agent under clinical investigation if no agents are approved locally; the imaging agent must remain unchanged for an individual subject throughout the study. A PET scan will only be performed at an ED Visit if the subject has been treated with study drug for at least 39 weeks.
- ^u Site staff will contact the subject or the study partner the day before the PK blood sampling to provide instructions that subjects must not take their study drug at home on the day of the PK blood

sampling. During this telephone contact with the subject or the study partner, the site staff should document the time that the subject took their study drug that day, ie, the day before the PK blood sampling.

- v Two plasma PK samples will be obtained: 1 sample at predose (trough) and another sample 1 to 6 hours postdose at Visits 3, 4, 6, 7, 9, and 11 and another sample 4 to 8 hours postdose at Visit 13 (or ED). Therefore, subjects or their study partners must be instructed not to take their study drug at home on the day the PK sampling is performed. Instead, subjects will take the study drug at the clinic after collection of the predose PK sample. At Visit 13 (or ED) the PK blood sample should be collected shortly before or after completing the LP for subjects participating in the CSF substudy. If at an ED Visit, the subject has already stopped study drug, then no dosing will take place, but the trough PK sample will still be collected. For subjects participating in the CSF substudy who have stopped taking study drug prior to the ED visit, the LP should be performed at approximately the same time as at the Screening Visit, and then a trough PK sample will be collected either shortly before or shortly after the LP.
- w PD and exploratory biomarker blood samples should be collected at fasting or at least 2 hours after the most recent meal and, as far as is feasible, samples should be taken at the same time of day at all visits. Samples should be taken predose at Visits 3, 4, 6, 7, 9, 11, and 13 (or ED).

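### For CSF-substudy subjects dosed at Visit 13, the baseline and Visit 13 plasma PD samples fall about 3 to 9 hours or more apart in clock time, and no plasma PD sample accompanies the Visit 13 CSF

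*Protocol*

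**What the plan says.** All references are to the protocol text as amended (Amendment 01).

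- **Screening plasma PD.** Section 9.5.2.1, Table 2 note j applies as follows: "For subjects who are going to provide a CSF sample at Tier 5 for amyloid eligibility and/or PD baseline purposes", the "blood draw for PD and exploratory biomarkers should be at approximately the same time of day as planned for the LP".
- **On-treatment plasma PD.** Table 3 note w: "Samples should be taken predose at Visits 3, 4, 6, 7, 9, 11, and 13 (or ED". Section 9.5.1.4.2 gives the same predose rule. Note w also asks that, "as far as is feasible, samples should be taken at the same time of day at all visits".
- **Visit 13 CSF.** Table 3 note x, which covers longitudinal CSF-substudy participants: "A CSF sample will be collected by LP between 4 and 8 hours postdose and at the same time of day", with the reference time and tolerance given as the "Screening LP (± 1 hour".
- **Visit 13 plasma PK.** Section 9.5.1.4.1 and note v, for substudy subjects: "At Visit 13 (or ED) the PK blood sample should be collected shortly before or after completing the LP".
- **Synopsis, Bioanalytical Methods.** Plasma Aβ(1-x) and other relevant biomarkers "will be measured in the blood samples collected at times that match the PK draws and during the Followup Period".
- **Baseline.** Table 3 has no PD blood draw at Visit 2, so Screening is the only scheduled pretreatment plasma PD sample.

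**The concern.** Each timing rule is reasonable alone, but together they pull the baseline and on-treatment plasma samples to different parts of the day. The Screening sample is tied to the LP clock time. The Visit 13 LP is tied both to that same clock time and to a window after the dose. The Visit 13 PD sample is tied to the time before the dose. A site that follows all three cannot also keep plasma PD at one time of day, and there is no Visit 2 sample to fall back on.

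What is at stake is the within-subject change in plasma Aβ(1-x). Section 9.4.6 uses PK and PD data to judge whether effects resemble those in earlier studies, and the first exploratory objective in Section 8.3 relates exposure and PD, in CSF and plasma, to efficacy and safety. In these subjects a change from baseline would combine any drug effect with any time-of-day effect. The on-treatment relation between plasma and CSF Aβ would compare a trough plasma sample with CSF taken hours after the dose.

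**Working it through.** **The protocol's own count first.** Table 4 lists 10 PD collection time points and 132 mL. Table 3 has PD draws at Visits 3, 4, 6, 7, 9, 11, 13, 14 and 15, which is 9. With Screening, 1 + 9 = 10. Volume: 1 × 24 + 9 × 12 = 24 + 108 = 132 mL. Both figures reproduce.

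**Clock gap.** Define:

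- T = clock time of the Screening LP; the Screening PD draw is at about T (note j)
- e = Visit 13 LP time minus T, between −1 h and +1 h (note x)
- h = time from the Visit 13 dose to the Visit 13 LP, between 4 h and 8 h (note x)
- d = time from the predose PD draw to the dose, 0 h or more (note w)

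Then:

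- Visit 13 LP = T + e
- Visit 13 dose = T + e − h
- Visit 13 PD draw = T + e − h − d
- Gap = T − (T + e − h − d) = h − e + d

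Results:

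- Smallest: 4 − 1 + 0 = 3 h
- Largest at d = 0: 8 − (−1) + 0 = 9 h
- With an assumed lead of d = 1 h: up to 9 + 1 = 10 h

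No permitted combination of h, e and d gives a gap near zero. The only slack is the word approximately in note j.

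**Interval between plasma PD and CSF at Visit 13.** This is h + d, so 4 to 8 h plus the predose lead.

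**After adding a PD tube at the Visit 13 LP.** The sample is at about T + e, so its clock difference from the Screening sample is |e|, about 0 to 1 h, and it sits beside the CSF.

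**Synopsis against the notes.** PK is drawn both predose and postdose at each treatment visit with PK sampling (Section 9.5.1.4.1). The Synopsis ties Aβ(1-x) to the PK draws without saying which. Note w and Section 9.5.1.4.2 allow predose only.

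**The case against.** The case for leaving the plan alone has several sound parts.

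- **A plasma sample is taken with the Visit 13 CSF.** A reader might infer that the CSF has no plasma partner at all. That is wrong: the PK sample is drawn around the LP. Only a plasma PD sample is missing. The main PK/PD analysis in Section 9.7.1.7.2 relates CSF biomarkers to plasma PK parameters or CSF drug concentrations, and this schedule serves it.
- **Screening has no simultaneous pair either.** A reader might infer that a matched plasma–CSF pair exists at baseline and is lost at Visit 13. The Screening PD blood is a Tier 3 procedure and the LP is Tier 5, after MRI eligibility is confirmed. Note j aligns clock time only.
- **Not every CSF giver is affected.** Subjects who give CSF for eligibility need not join the substudy, and without a Visit 13 LP no gap is fixed for them. Subjects at an early discontinuation visit who have already stopped drug are not dosed, so the 4 to 8 hour window does not apply.
- **Table 4 does not prove one PD draw per visit.** Its PK row also counts 7 time points, although two PK samples are taken at each of those visits. The point rests on the predose rule instead.
- **Food is not part of the problem.** Notes j and w set the same condition: fasting, or at least 2 hours after a meal.
- **The wording is soft.** Note w says should, and asks for constant timing only where feasible.
- **Placebo subjects follow the same schedule**, so a time-of-day shift can be separated from the drug effect between arms.

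All of this limits the scope, and the last point protects the arm comparison. It does not remove the conflict. The feasibility qualifier gives no real relief when the protocol's own LP timing makes compliance impossible for these subjects. The placebo arm also does not restore an individual subject's change from baseline, because the gap itself varies from 3 to 9 hours or more between subjects. A predose trough series is a legitimate choice and can be kept.

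**Conclusion.** The point holds for longitudinal CSF-substudy subjects who are dosed at Visit 13. Their baseline and Visit 13 plasma PD samples are about 3 to 9 hours apart in clock time, plus any predose lead. The same-time-of-day request cannot be met between those two visits, and no plasma Aβ(1-x) sample accompanies the Visit 13 CSF.

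The arithmetic assumes that the Screening LP takes place at its planned time, that the PD draw is at that clock time, and that notes w and x are followed as written.

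The consequence is confined to within-subject plasma PD change and exploratory plasma PK/PD. A reader might infer that an efficacy or biomarker endpoint is compromised; the documents do not support that. The primary endpoint does not use these samples. The biomarker endpoints in Section 9.7.1.1.4 include CSF Aβ but no plasma Aβ, and the CSF samples are matched within 1 hour. Between-arm plasma comparisons are not biased, because both arms share the schedule. Nor do the documents give any figure for time-of-day variation in plasma Aβ, so the gap is established but the size of any resulting distortion is not.

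**What to change.** 1. Reconcile Table 2 note j with Table 3 notes w and x (and Section 9.5.1.4.2), stating which plasma PD samples are meant to share a clock time in substudy subjects.
2. For substudy subjects dosed at Visit 13, add one PD tube to the postdose PK draw already taken around the LP. Use it for change from the LP-timed Screening sample and for comparison with the CSF.
3. Keep the predose series unchanged for trough comparisons.
4. Amend the Synopsis sentence so that it says which PK draws the PD samples match.

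Cost: one extra tube at one visit for these subjects, from a venepuncture that already happens, and an update to Table 4. At the Table 4 volume of 12 mL, the PD total for a substudy subject becomes 132 + 12 = 144 mL, and total blood becomes 627 + 12 = 639 mL.

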All subjects who discontinue study drug before reaching 12 months of treatment will also be asked to return to the clinic for a 12-month clinical assessment and then again at 24 months. Subjects who discontinue treatment between 12 and 24 months of treatment will be asked to return to the clinic for a 24 month clinical assessment. Subjects who discontinue early from study drug are considered “on study” as long as they continue to return for their regularly scheduled clinical assessments at 12 and 24 months as outlined above, at which efficacy and quality of life will be assessed along with concomitant medications and AEs. However, subjects who discontinue study drug early are not considered to have ‘completed’ the study as a final Subject Disposition.

The primary reason for discontinuation and all other reason(s) contributing to the subject’s discontinuation from study drug(s) should be collected on the ED from study drug electronic case report form (eCRF) page. In addition, the date of last dose of study drug(s) will be recorded on the Study Drug Dosing eCRF page. If a subject discontinues study treatment and the study at the same time, the end-of-study procedures (Final Visit) will be followed (see [Section 9.5.5](#)).

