^b Subjects who discontinue taking study drug prematurely for any reason will undergo an ED Visit within 7 days of their last dose of study drug. In addition, Follow-Up Visits will be scheduled 4 and 12 weeks after the last dose of study drug (Visit 14 and Visit 15, respectively). Subjects who discontinue study drug before reaching 12 months of treatment will also be asked to return to the clinic for a 12 month clinical assessment and then again at 24 months. Subjects who discontinue treatment between 12 and 24 months of treatment will be asked to return to the clinic for a 24 month clinical assessment. Subjects who discontinue early from study drug are considered “on study” as long as they continue to return for their clinical assessments at 12 and 24 months as outlined above, at which efficacy (MMSE, CDR, ADAS- cog₁₄) and quality of life (EQ-5D, QOL-AD and Zarit’s Burden Interview) will be assessed along with concomitant medications and AEs. These 12 and 24 month clinical assessment visits do not need to be attended if they fall within 8 days (visit window) after the ED Visit or within ±8 days of either of the Follow-Up Visits (Visit 14 and Visit 15).

^c All subjects, regardless of whether they complete all 24 months of treatment or discontinue study drug prematurely, will complete 2 posttreatment Follow-Up Visits; one 4 weeks after the last dose of study drug and a second 12 weeks after the last dose of study drug (Visit 14 and Visit 15 respectively). If clinically indicated, more frequent safety assessments can be made as UNS assessments or visits during the posttreatment Follow-Up Period. Subjects who have a Grade 2 or greater lymphocytopenia (less than 800/mm³) during the follow-up period (ie, at either Visit 14 or Visit 15) should have ALC measured every 4 weeks until resolution or confirmation of a non drug-related cause of the lymphocytopenia. ALC will be derived from the CBC with differential representing the normal lymphocytes (with atypical lymphocytes removed and presented as a separate count if they are present) and calculated by the white blood cell count × percentage of lymphocytes. (revised per Amendment 01)

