9.7.1.1.2 SECONDARY ENDPOINTS

The secondary endpoints of the study are:

- Time to worsening of CDR scores by 24 months (eg, the worsening of global CDR score is defined as an increase from baseline by at least 0.5 points on the global CDR scale on 2 consecutive scheduled visits at which global CDR is undertaken)
- Time to conversion to dementia for subjects who were not clinically staged as dementia at Baseline based on clinical diagnosis
- The rate of change over time (mean slope) based on CDR-SB score over 24 months
- Change from baseline in CDR-SB at 27 months (ie, 24 months of treatment plus 3 months posttreatment follow-up)
- Change from baseline in ADAS-cog₁₄, MMSE, and FAQ at 24 months
- Change from baseline in ADAS-cog₁₄ Word List (immediate recall and delayed recall) at 24 months

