9.7.1.6.2 SECONDARY EFFICACY ANALYSES

The secondary analyses will be performed only if the primary analysis is significant. The treatment effect for elenbecestat (E2609) 50 mg/day versus placebo, for each secondary efficacy endpoint, will be tested using a sequential testing procedure at a significance level of 2-sided alpha = 0.05, ie, any test will start only if the test with higher hierarchical order is

significant. The final hierarchical order will be specified later in the statistical analysis plan before database lock.

Time to worsening of CDR scores by 24 months will be analyzed on the FAS using Cox regression model for treatment effect adjusting for randomization stratification factors. Time to worsening of a CDR score is defined as time from randomization to worsening of the CDR score (ie, the first worsening in 2 consecutive scheduled visits). For subjects whose CDR scores have not worsened by the end of study, the time to worsening of the CDR score will be censored at the date of last CDR assessment for these subjects.

Time to conversion to dementia for subjects who were not clinically staged as dementia at Baseline based on clinical diagnosis will be analyzed on the FAS using Cox regression model for treatment effect adjusting for randomization stratification factors. Proportion of subjects with dementia diagnosis at 24 months will be estimated using Kaplan—Meier method based on time to conversion to dementia based on clinical diagnosis. Time to conversion to dementia for subjects who were not clinically staged as dementia at Baseline based on clinical diagnosis is defined as time from randomization to conversion to dementia based on clinical diagnosis. For subjects without clinical dementia by the end of study, the time to conversion to dementia based on clinical diagnosis will be censored at the date of last dementia diagnosis.

The rate of change over time (mean slope) based on change from baseline in the CDR-SB will be analyzed using linear mixed effects (LME) models for multivariate normal data derived from a random coefficient model (slope analysis), where the mean slope in each group depends on a continuous assessment time. The LME model will include baseline CDR-SB, randomization stratification variables, assessment time, and treatment group-by-assessment time.

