The other continuous secondary efficacy endpoints as defined above will be analyzed using the same MMRM model as the primary efficacy analysis to compare elenbecestat (E2609) 50 mg per day versus placebo on the FAS, using baseline value corresponding to the response variable in the model.

The relationship between clinical changes at 24 months (CDR-SB, ADAS-cog₁₄, MMSE, and FAQ) and changes in each of the biomarkers (amyloid PET, CSF t-tau and p-tau, vMRI, and fMRI) at 24 months, will be evaluated using an ANCOVA model. Changes in clinical scales at 24 months will be the response variables and either continuous or categorical change of biomarkers will be independent variables. The ANCOVA model will also include baseline value for clinical scale as a covariate, randomization stratification variables, treatment group as factors, and other terms as appropriate.

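### The itemised list for the off-drug 12- and 24-month visits leaves out the FAQ and disease staging, so two secondary endpoints lose off-drug follow-up that CDR, MMSE and ADAS-cog14 keep

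*Protocol*

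**What the plan says.** Note b to Table 3 (section 9.5.2.1) describes the 12- and 24-month assessments of subjects who have stopped drug as visits "at which efficacy (MMSE, CDR, ADAS- cog₁₄) and quality of life" are assessed. It completes the list with "EQ-5D, QOL-AD and Zarit’s Burden Interview) will be assessed along with concomitant medications and AEs". Neither the FAQ nor disease staging appears.

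The body text has no such list. Section 9.3.3 describes the same visits as ones "at which efficacy and quality of life will be assessed along with concomitant medications and AEs"; section 9.5.5 and the synopsis (Conduct of the Core Study) say the same in substance.

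The grid of Table 3 places the FAQ at Visits 2, 7, 9, 11 and 13, at the early discontinuation (ED) visit, and at Visits 14 and 15. It places staging at Visits 6 to 13, at ED and at Visit 15. Note o asks for staging every 3 months. For subjects who stop early, "Follow-Up Visits will be scheduled 4 and 12 weeks after the last dose of study drug (Visit 14 and Visit 15, respectively"). The 12- and 24-month visits "do not need to be attended if they fall within 8 days (visit window) after the ED Visit or within ±8 days" of Visit 14 or 15.

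Section 9.7.1.1.2 lists as secondary endpoints the 24-month change in FAQ, in the same bullet as ADAS-cog14 and MMSE, and "Time to conversion to dementia for subjects who were not clinically staged as dementia at Baseline based on clinical diagnosis". Under section 9.7.1.6.2 the FAQ "will be analyzed using the same MMRM model as the primary efficacy analysis", on the FAS. Where a subject has not converted, the rule is that "the time to conversion to dementia based on clinical diagnosis will be censored at the date of last dementia diagnosis". Both endpoints belong to the sequential testing procedure.

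**The concern.** The off-drug visits exist so that follow-up continues after treatment stops. Section 9.7.1.6.1 bases the primary analysis on an intent-to-treat principle regardless of adherence, and the FAQ is to be analysed with the same model. Note b retrieves the off-drug data for CDR, MMSE and ADAS-cog14, and for three quality-of-life and burden scales that are only exploratory. It does not retrieve them for the FAQ or for staging, which are secondary.

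Two consequences follow. For the FAQ, the 24-month value in most discontinuers would be inferred by the model from earlier values, whereas for ADAS-cog14 and MMSE it would be observed in those who return. One testing sequence would then mix endpoints that use off-drug outcomes with endpoints that largely do not.

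For time to conversion, a subject who stops drug is censored about 12 weeks later even if seen again, with a CDR, at 12 or 24 months. Sections 9.3.3 and 9.5.1.5.5 require permanent discontinuation in certain cases of lymphocytopenia, rash and herpes. Section 7.1 reports rash, herpes relapse and lymphocyte reductions in the multiple-dose study. Discontinuation that differs by arm is therefore plausible, though not established, and the censoring could be informative. An analysis plan cannot supply assessments that were never made.

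**Working it through.** **Schedules side by side (Table 3 and note b)**

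| Assessment | On treatment | ED | Visit 14 | Visit 15 | Off-drug 12/24 months (note b) |
|---|---|---|---|---|---|
| CDR | every 3 months | yes | yes | yes | named |
| MMSE, ADAS-cog14 | every 6 months | yes | yes | yes | named |
| FAQ | every 6 months | yes | yes | yes | not named |
| Disease staging | every 3 months | yes | no | yes | not named |

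**The plan's own figure.** Section 9.7.2 gives a placebo mean change of 1.75, SD 2.05, a 25% reduction, 90% power, two-sided 0.05, 30% dropout and 1330 subjects.
- Difference: 0.25 × 1.75 = 0.4375.
- Normal approximation: n = 2 × (1.960 + 1.282)² × 2.05² / 0.4375², which gives 462 per arm; 462/0.7 = 660, total 1320.
- Exact t-test: 463 per arm; 463/0.7 rounds up to 662, total 1324.
- With 665 × 0.7 = 465.5 per arm, power is 90.2%.

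The stated 1330 is reproduced. It matters here only as the source of the 30%.

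**FAQ at month 24**
- Assumption A: the 30% is drug discontinuation. 0.30 × 1330 = 399 discontinuers.
- Assumption B: last-dose days are spread evenly over the 728 days before day 729, with ED on the last-dose day.
- The 24-month visit is waived, and an FAQ is taken at a nearby visit instead, if the last dose falls on days 721–728 (ED, 8 days), 693–709 (Visit 14, 17 days) or 637–653 (Visit 15, 17 days). That is 42/728 = 5.8%, or about 23 of 399. Placing ED 7 days after the last dose gives 43/728 = 5.9%, again about 23–24.
- Remaining: 399 − 23 = 376 with no 24-month FAQ called for.
- Assumption C: 50–80% of these return. 376 × 0.5 = 188 and 376 × 0.8 = 301, so roughly 190–300 subjects attend a 24-month visit with CDR, MMSE and ADAS-cog14 but no FAQ. The full return range of 25–100% gives 94–376.

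**Staging time lost before month 24**
- The last staging for a discontinuer is at Visit 15, 84 days after the last dose L. Days lost = max(0, 729 − (L + 84)).
- Even spread: time is lost when L is 644 or less, 644/728 = 88%. The mean over all discontinuers is (644 × 645/2)/728 = 285 days, or 285/30.4 = 9.4 months.
- Exponential stopping with 30% by month 24: 90% lose some time, with a mean of 10.1 months.
- Share of all planned staging time (even spread): 0.30 × 285/728 = 12%. This supposes that the time could otherwise be covered; staging at the 12- and 24-month visits recovers it only for those who return.

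**Missed conversions, for scale only.** The protocol gives no conversion rate. Assume 75% of the 399 are non-demented at baseline (299), 50–80% return, and conversion is 15–25% a year. Counting only subjects still unconverted when staging stops, about 15–39 conversions fall after the last staging in subjects who return. With full follow-up, 0.75 × 1330 = 998 non-demented subjects would yield 998 × (1 − 0.85²) = 277 to 998 × (1 − 0.75²) = 436 conversions. The loss is then about 15/277 = 5% to 39/436 = 9%.

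**The case against.** **The omission may not be intended.** The body text says efficacy without restriction, section 9.5.1.3.1 describes the FAQ among the efficacy scales, and note o asks for staging every 3 months. This stands as an explanation: a drafting gap is at least as likely as a choice. It does not remove the problem, because note b is the only itemised instruction and the protocol disagrees with itself on what is collected.

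**A reader might infer that every discontinuer lacks both endpoints.** The documents do not support that. Subjects who stop shortly before month 24 have an FAQ at ED, Visit 14 or Visit 15, and staging at ED or Visit 15. Those whose last dose falls in the final 12 weeks lose no staging time before month 24. Earlier, ED and follow-up FAQ values exist for the others; only the 24-month value is not called for. Conversions seen up to Visit 15 count as events, so this endpoint is censored early, not absent.

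**A reader might also take all 399 as the number harmed.** Section 9.7.2 uses the 30% to inflate a comparison of 24-month CDR-SB, so on its own terms those subjects supply no 24-month CDR either. The affected group is those who stop drug and return, and the protocol gives no figure for it. This objection stands in full, which is why the size is given as a range resting on stated assumptions.

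**The primary endpoint is untouched.** CDR is collected at these visits, and the secondary endpoints are tested only if the primary succeeds. The intent-to-treat principle is also stated only for the primary analysis. These points limit the severity.

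**Later text may differ.** The synopsis already carries a reference to Amendment 02, so note b may have been changed since. That cannot be checked from this document.

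**Conclusion.** The point holds as an inconsistency with a real data-collection consequence, of moderate severity. Note b omits the FAQ and disease staging from the off-drug 12- and 24-month visits, while the body text and note o point the other way.

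Followed literally, note b leaves most returning discontinuers without a 24-month FAQ: roughly 190–300 subjects, if 30% discontinue drug, stopping times are evenly spread and 50–80% return. It also ends staging about 12 weeks after the last dose. About 88–90% of discontinuers lose some staging time, averaging 9–10 months across all of them. Time to conversion is censored early and possibly informatively; whether the arms would differ is unknown. Any count of missed conversions depends on rates that the protocol does not give. The primary analysis is not affected.

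**What to change.** Add the FAQ and disease staging, with the existing central review and adjudication, to the list in note b for the off-drug 12- and 24-month visits. Align the synopsis and sections 9.3.3 and 9.5.5 so that all four places name the same assessments. The censoring rule in section 9.7.1.6.2 needs no change, since the new staging dates become the last assessment automatically. If the sponsor does intend to omit these items, the body text should say so and state how the two endpoints are then to be interpreted.

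The cost is small. The visit already takes place and the study partner already contributes to the CDR, so the addition is a 10-item partner questionnaire and one staging entry sent to central review. It has to be made while subjects are still in follow-up, because assessments not made then cannot be recovered.
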